The calculation of sample size was based on the question: "Which of the applied caries treatment methods will have the least frequency of complication occurrences, treating severe early childhood caries in children from the ages of 2 to 6 years-old?" Since we will compare proportions in six groups, in the sample size calculation we used formulas, which are shown in Fig 1 (Shao, Chow and Wang, 2003), calculating that the planned number of various proportions for comparison will be 9.

From previous studies it is known that conventionally treating early childhood tooth caries, the frequency of complications is 10% (Innes *et al.*, 2013), but, examining clinical cards at RSU's Institute of Stomatology Children's Dentistry department, the frequency of complications for children that are waiting in line for treatment with general anaesthesia and who receive no additional treatment, is approximately 30%, therefore in the study's treatment groups we expect that the frequency of complications will be no greater than 10%, but in the placebo groups - 30%. From the calculations in the formulas above, we calculated, that for the study we need 49 children in each group, to ascertain the difference in complication proportions between 30% un 10% with α error 0.05 and with a study capacity of 80%. Together 294 children are necessary but, calculating possible losses during the observation time, it is planned to involve 70 children in each group, therefore, 420 in six groups.

$$n = (p_A(1 - p_A) + p_B(1 - p_B)) \left(\frac{z_{1-\alpha/(2\tau)} + z_{1-\beta}}{p_A - p_B} \right)^2$$

$$1 - \beta = \Phi(z - z_{1-\alpha/(2\tau)}) + \Phi(-z - z_{1-\alpha/(2\tau)}) \quad , \quad z = \frac{p_A - p_B}{\sqrt{\frac{p_A(1-p_A)}{n} + \frac{p_B(1-p_B)}{n}}}$$

Fig 1. Formulas to calculate the sample size. n = the sample size (for one comparison, therefore two equivalent groups); Φ = standard normal allocation function; α = I type error; τ = number of comparisons; β = II type error; $1-\beta$ = study capacity.

Randomization, allocation and blinding

Flow chart of research methodology is shown in Fig 2. If the patient fulfills the inclusion criteria, their parents (caregiver) will be offered the opportunity to participate in the study. The objective of the study will be explained both verbally and in writing, as well as the expected results and side effects of the treatments:

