- 4) the level and development of the caries damage and activity (ICDAS, Nyvad criteria).

Outcome measures:

- I. Primary outcome measures:
 - A. Pain history during the observation period, assessed as Yes/No at 12 months follow-up visit.
 - B. Abscess history during the observation period, assessed as Yes/No at 12 months follow-up visit.
 - C. The number of newly extracted or otherwise surgically treated teeth during the observation period, assessed as a number of extracted teeth during the last year at 12 months follow-up visit.
- II. Secondary outcome measures:
 - A. The change in the overall activity of caries as Active/Non-active, assessed at 12 months follow-up visit.
 - B. The progression and change of activity of every lesion, assessed by ICDAS (for progression) and Nyvad (for activity) criteria, at 12 months follow-up visit.
 - C. The parent’s satisfaction with the way their children’s teeth look, assessed by questionnaire, asking: “Are you satisfied with the way your child’s teeth look?”

- and “Would you agree to repeat the treatment procedure used?”, both measurements in 5-point Likert scale, assessed at 12 months follow-up visit.
- D. The child’s satisfaction with their teeth, measured by the visual analogue scale (VAS) with 3 points - happy, not sure, sad, assessed at 12 months follow-up visit.
 - E. The child’s feelings during the treatment, measured by the modified Wong-Baker scale with 3 options - no hurt, hurts a little, hurts a lot), assessed during every appointment (depending on treatment group can be assessed at baseline, 1, 2, 3 weeks and 12 months; or at baseline, 6 and 12 months).
 - F. The direct costs of the treatment and the cost-effectiveness, calculated as EUR spent per treatment protocol; EUR per prevented major complications (in patient-level - pain, abscess, extraction) and EUR per prevented minor complications (in tooth-level - progression of caries lesion), the calculation will be made at 12 months follow-up.
 - G. The treatment method’s undesirable side effects, assessed by parents’ questionnaire at the 12 months follow-up visit.

Statistical analysis

Data will be digitized, by entering in an ad-hoc form in the Google Docs programme. Further the data will be exported cvs (comma separated values) to an archive. Missing data will be eliminated from the analyses, marking them NA.

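### The trial is sized on one complication proportion that is none of its three declared primary outcomes, so the stated alpha and power attach to none of them

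*Protocol*

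**What the plan says.** Protocol, Sample size calculation: the question behind the calculation is "Which of the applied caries treatment methods will have the least frequency of complication occurrences". The text then says that proportions in six groups will be compared and sets the number of comparisons at 9. It expects that in the treatment groups "the frequency of complications will be no greater than 10%, but in the placebo groups - 30" per cent, and derives 49 children per group "with α error 0.05 and with a study capacity of 80" per cent. Complication is not defined there.

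Protocol, Outcome measures, I: three primary outcomes are listed with no ranking and no rule for combining them.
- Item I.A is "Pain history during the observation period, assessed as Yes/No at 12 months follow-up visit".
- Item I.B has the same form for abscess: a yes-or-no answer per child, taken at the same visit.
- Item I.C is of another kind, a tally of teeth per child: "The number of newly extracted or otherwise surgically treated teeth during the observation period".

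Protocol, Outcome measures, II.F (a secondary cost item): "EUR per prevented major complications (in patient-level - pain, abscess, extraction". This is the only place where the components of a patient-level complication are named.

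The primary aim under Work packages, WP4, and the recruitment item under Risks, 1a, also speak of complications collectively. Risks, 1a repeats the 10% and 30% rates.

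**The concern.** A sample size calculation protects a trial only if its outcome is the one on which the trial will be judged. Here the aim, the assumed rates, the alpha and the power all refer to one complication proportion, while the primary list contains three other variables. Two consequences follow.

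First, the correction for 9 is introduced by the number of groups. If it covers group comparisons only, three primary outcomes are tested under a correction meant for one. The trial could then claim success on recalled pain while abscess and extraction show nothing.

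Second, nothing in the document supports 30% against 10% for pain alone or for abscess alone, and the third outcome is not a proportion at all.

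**Working it through.** **Inputs.** From the Sample size calculation: pA = 0.30, pB = 0.10, alpha = 0.05 two-sided, power 80%, τ = 9, 49 per group. From Outcome measures, I: three primary outcomes. Not in the documents, and so assumed where used: which nine comparisons are meant, the success rule, the correlation between outcomes, and the rates of the single components.

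**1. The protocol's own figure.** Fig 1 gives n = [pA(1−pA) + pB(1−pB)] × [(z(1−α/2τ) + z(1−β)) / (pA−pB)]².
- Variance term: 0.21 + 0.09 = 0.30, and 0.30 / 0.20² = 7.5.
- With τ = 9: z(1−0.05/18) = 2.773 and z(0.80) = 0.842, so n = 7.5 × 3.615² = 98.0.
- The stated 49 is half of this. The companion power formula in Fig 1 divides each variance by n separately, so n is per group.
- At 49 per group that power formula gives z = 0.20 / √(0.30/49) = 2.556 and power Φ(2.556 − 2.773) = 41%.

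The fall from 80% to 41% is thus a separate error. It is shown here only so that it is not charged to the present point.

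**2. Match between the powered and the declared outcomes.**

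| Variable | Type | Declared primary? | Sized by Fig 1? |
|---|---|---|---|
| Complication, 30% vs 10% | proportion | no | yes |
| Pain (I.A) | proportion | yes | no rates given |
| Abscess (I.B) | proportion | yes | no rates given |
| Extracted or surgically treated teeth (I.C) | count | yes | formula does not apply |

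**3. Family-wise error**, if all nine comparisons are made on each outcome at 0.05/9 and any one success counts.
- Tests: 3 × 9 = 27.
- Bonferroni bound: 27 × 0.05/9 = 15%.
- All tests independent: 1 − (1 − 0.05/9)^27 = 14.0%. The nine tests of one outcome give 1 − (1 − 0.05/9)^9 = 4.9%.
- Simulation (300,000 runs) with nine assumed contrasts: three agent pairs within each of the two schedules, plus three contrasts between schedules. One outcome alone gives about 4.2%.

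| Correlation between outcomes | Error, any of three |
|---|---|
| 0 | 12.1% |
| 0.5 | 11.2% |
| 0.7 | 10.0% |
| 0.9 | 7.7% |

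**4. Including the outcomes in the correction (τ = 27)**, with 30% vs 10% assumed for every outcome: z(1−0.05/54) = 3.113 and n = 7.5 × (3.113 + 0.842)² = 117.3, so 118 per group instead of 98. At 49 per group, power goes from 41% to 29%.

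**5. Power for one component** at 49 per group and τ = 9, with assumed rates.
- 15% vs 5%: variance term 0.1275 + 0.0475 = 0.175; z = 0.10 / √(0.175/49) = 1.673; power Φ(1.673 − 2.773) = 14%.
- 25% vs 5%: variance term 0.1875 + 0.0475 = 0.235; z = 0.20 / √(0.235/49) = 2.888; power Φ(2.888 − 2.773) = 55%.
- For comparison, 30% vs 10%: 41%.

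**The case against.** A reader might infer that the error rate is simply tripled. The documents do not support that as a fact. It needs all nine comparisons repeated for each outcome, success on any single outcome, and weak correlation between outcomes. The protocol states none of these, and pain, abscess and extraction in the same child are plausibly correlated. The nine are never listed, so they might already count outcomes (three outcomes by three contrasts), in which case the error claim would fall. That reading has little behind it, since the 9 follows directly from the remark on six groups and one of the three outcomes is not a proportion, but it cannot be excluded.

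A reader might also infer that each component must be rarer than the composite and therefore has less power. Neither step holds. A component cannot be more frequent than a composite that contains it, but it can equal it. A rarer component can also have more power: if 5% of children in each arm have only some other complication, a 25% vs 5% component sits inside a 30% vs 10% composite and has 55% power against 41%.

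A decision rule across outcomes may stand in an analysis plan that is not at hand, and its absence here is not a fault. Such a rule could control the error rate. It would not turn the powered proportion into a declared primary outcome. That mismatch lies within the protocol, and this part of the concern stands in full.

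**Conclusion.** The point holds. The proportion that carries the aim, the 30% and 10%, the alpha and the power is undefined and is not among the three primary outcomes, one of which is a count. This rests on the text alone and needs no assumption.

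The size of the consequence is conditional. Under the three conditions in step 3 of the working, family-wise error is 14–15% at the upper end and roughly 8–12% in the simulation, against a stated 5%. Power for pain or abscess alone is unknown, not shown to be low: 14% and 55% are illustrations under assumed rates. Of the fall to 29% under τ = 27, only the step from 41% belongs to this point; the step from 80% to 41% comes from using 49 where the formula gives 98.

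Because it decides what counts as trial success, the mismatch has to be settled before outcome data are seen by group.

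**What to change.** 1. Define one primary outcome: the child had at least one major complication (pain, abscess, or extraction or other surgical treatment of a tooth) within 12 months, Yes/No. Item II.F names pain, abscess and extraction but does not define such a variable, so the definition must be written out.
2. Confirm that the 30% from the clinic's records and the 10% from the cited source refer to this definition; if not, revise the rates and the size.
3. List the nine group comparisons that τ covers.
4. Report pain, abscess and number of extracted or surgically treated teeth as key secondary outcomes by group with confidence intervals. The composite can still be won on pain alone, and this makes such a result visible.

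All components are already collected at the 12-month visit, so this change is one of wording. The price is that no component carries a separate confirmatory claim. If separate claims are wanted, the alternative is to count the outcomes in τ, size the tooth count by a method for counts, and give rates for pain and abscess. With 30% vs 10% assumed throughout, that raises the formula's requirement from 98 to 118 per group. Neither route repairs the halved sample size: the composite at τ = 9 still needs 98 evaluable children per group, or 98/0.70 = 140 with the planned 30% loss.

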1. The first placebo group – placebo varnish application twice with a six-month interval and a recommendation to brush teeth with a toothpaste containing fluoride (F content of at least 1000 ppm);
2. The second placebo group – placebo varnish application four times with a week's interval and a recommendation to brush teeth with a toothpaste containing fluoride (F content of at least 1000 ppm);
3. The first SDF group – Riva Star SDF (35-40% silver fluoride, 15-20% ammonium) application twice with a six-month interval and a recommendation to brush teeth with a toothpaste containing fluoride (F content of at least 1000 ppm);
4. The second SDF group - Riva Star SDF application four times with a week's interval and a recommendation to brush teeth with a toothpaste containing fluoride (F content of at least 1000 ppm);
5. The first Tiefenfluoride group – Tiefenfluoride (0,4% $\text{CuSiF}_6 \times 6 \text{H}_2\text{O}$, 10,9% $\text{MgSiF}_6 \times 6 \text{H}_2\text{O}$, 0,1% NaF, 9,6% $\text{Ca}(\text{OH})_2$) application twice with a six month interval and a recommendation to brush teeth with a toothpaste containing fluoride (F content of at least 1000 ppm);
6. The second Tiefenfluorid group - Tiefenfluorid application four times with a week's interval and a recommendation to brush teeth with a toothpaste containing fluoride (F content of at least 1000 ppm);

The goal of the treatment is to stop the progress of the existing damage progress and avert the formation of new damage; caries tissue removal will not be performed; the products will be applied to dried teeth.

For ethical reasons, the negative control group will not be used – in each of the study’s groups the parents (direct caregivers) will be given advice about tooth cleaning and diet, using motivational intervention principles and recommending brushing teeth with toothpaste that contains fluoride (at least 1000 ppm), which is defined as non-restorative caries treatment and which has also proven its effectiveness in stopping caries damage.

Outcome variables

Patients will be examined at the baseline and at 12 months.

The patient’s primary examination will determine the following parameters:

- 1) general information about the child (birth date, gender, medical health history);
- 2) hygiene and dietary habits (frequency of brushing teeth; are teeth cleaned by the child or by parents; the fluoride concentration in toothpaste);
- 3) plaque (visible/invisible);

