4. **WP4** Clinical trial. **The objective of WP4** is to perform the clinical trial according to an established protocol and the highest ethical standards with the primary aim of finding out which high-concentration fluoride application method and which application protocol more effectively protects pre-school children from complications arising from early childhood dental caries. Secondary objectives are to evaluate at which stage of development (cariou lesions) the methods are the most effective; which fluoride application method and protocol is more effective in arresting non-cavitated and cavitated cariou lesions in preschool children; how satisfied are parents and patients with SDF and Tiefenfluorid application procedures and side-effects (staining) and what are the costs and cost-effectiveness of each method and application protocol.
 1. Enrolment of patients in the study. General staff will offer suitable patients the chance to register for the procedures. A calibrated examiner (postdoctoral researcher) will inform parents about all details of the study. If the offered is accepted, parents sign the informed consent form.

2. Initial examination and interviewing of enrolled patients and their parents by a calibrated examiner (postdoctoral researcher).
3. Random allocation in six intervention groups. This will be done by a calibrated examiner (postdoctoral researcher) using six closed envelopes containing colour codes.
4. Performing interventions according to the protocol of each study group. Those interventions will be done by Intervention Staff (IS) - four trained postgraduate students and assistants (dental hygiene students).
5. Performing and documenting emergency treatment during the follow-up period. Done by trained general staff on a daily basis according to patient needs. Registration will be done using a pre-prepared form.
6. Follow-up examination. Done by calibrated examiner (postdoctoral researcher).

Deliverables of WP4

D4.1 Enrolment registration form.

D4.2 Signed informed consent forms.

D4.3 Initial patient examination forms (including parent questionnaire).

D4.4 Intervention registration forms (including Visual Analogue Scale [VAS] of patient satisfaction).

D4.5 Emergency treatment forms (including VAS of patient satisfaction).

D4.6 Follow-up examination forms (including VAS of patient acceptance and Likert scale questions of parents acceptance).

Milestones of WP4

MS4.1 Meetings about enrollment, randomization and allocation.

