D6.2 Conference abstracts.

D6.3 Publication about the effectiveness of SDF and Tiefenfluorid treatment in preschool children with S-ECC (to be published in Caries Research (impact factor: 2.188) or in BMC Oral Health (impact factor: 1.602).

D6.4 Publication about the effectiveness of fluoride treatment according to the type of carious lesion in deciduous dentition (to be published in the International Journal of Paediatric Dentistry (impact factor: 2.18) or in European archives of paediatric dentistry: official journal of the European Academy of Paediatric Dentistry (impact factor: 1.48).

D6.5 Evidence-based recommendations and economic evaluation report for national policymakers.

Milestones of WP6

MS6.1 Meeting with Communication Department and IT department of RSU.

MS6.2 Scientific conferences.

MS6.3 Meeting with policymakers.

Gantt chart

The workflow in each work packages and relevant deliveries are illustrated in the Gantt chart (Fig 4.).

[figure not shown]

Fig 4. The Gantt chart of the clinical trial.

Risks

1. Research achievability risks
 - a. Number of patients recruited less than expected - sample size calculation was estimated using conservative assumptions. The expected difference in the prevalence of severe caries complications in different treatment groups and the placebo group is expected to be 20% (10% complication rate for treatment groups and 30% for placebo). From previous studies, the expected prevalence in treatment groups could be even less, meaning the observed difference would be greater. In such a case, statistical power can be achieved even with a lower number of patients.
 - b. Loss of follow-up – we plan to include 70 patients in every group in order to ensure that there are still at least 49 in every group at the end of the project (we assume the potential loss of follow-up examinations to be 30%, which we consider to be sufficient).
2. Research methodology risks

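### Cost-effectiveness in outcome II.F reads as an average cost per complication prevented, which does not show what the two extra applications buy

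*Protocol*

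**What the plan says.** In the protocol's list of outcome measures, item II.F sets out the economic outcome: "The direct costs of the treatment and the cost-effectiveness, calculated as EUR spent per treatment protocol". It continues with two ratios: "EUR per prevented major complications (in patient-level - pain, abscess, extraction) and EUR per prevented minor complications", the second counted per tooth as lesion progression. The item does not say what a complication is prevented relative to, and it does not mention comparing one active protocol with another.

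Under Work packages, WP4 gives the question that these figures should answer: "what are the costs and cost-effectiveness of each method and application protocol". Under WP6, deliverable D6.5 is "Evidence-based recommendations and economic evaluation report for national policymakers".

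The Interventions section creates four active protocols: two products, each given either as "application twice with a six-month interval" or four times at weekly intervals. Each schedule has its own placebo group. For complications, the Sample size calculation section states that in the treatment groups "we expect that the frequency of complications will be no greater than 10%, but in the placebo groups - 30" per cent. Risks, item 1a, repeats that the difference "is expected to be 20% (10% complication rate for treatment groups and 30% for placebo" and adds that "the expected prevalence in treatment groups could be even less, meaning the observed difference would be greater". None of these rates distinguishes the two schedules, and no unit cost appears anywhere.

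**The concern.** An average ratio divides the whole cost of a protocol by everything that it prevents. That describes one protocol against doing without it. It does not help to choose among several active protocols. For that choice, the question is what the dearer protocol adds in cost and in effect over the next cheaper one.

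The two quantities can point in different directions. If four applications cost twice as much as two, they must prevent twice as many complications merely to tie on the average ratio. A schedule that prevents more at a price a funder might accept can therefore rank second. Conversely, a schedule whose extra visits achieve nothing still shows a finite ratio that may look acceptable. The economic report for policymakers could then rest on a number that does not answer the schedule question.

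The unnamed comparator adds a second problem. If each schedule is measured against its own placebo group, the two schedules' effects start from different observed baselines. If costs are also taken net of that placebo group, which has the same number of visits, the cost of the extra visits largely cancels.

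**Working it through.** **Inputs**

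- Placebo complication rate p0 = 30% and active rate at most 10%: Sample size calculation, and Risks 1a.
- Applications: 2 or 4 (Interventions).
- Costs: none in the protocol. Assumption: one unit per application, so C2 = 2 and C4 = 4. A range follows below.

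The protocol states no cost-effectiveness figure, so there is none to reproduce.

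**Formulas**

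- Average ratio for k applications: Ck / (p0 − pk).
- Incremental ratio, four against two: (C4 − C2) / (p2 − p4).

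**Results at p0 = 30%, in units per complication prevented**

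| Rate with 2 | Rate with 4 | Average, 2 | Average, 4 | Incremental |
|---|---|---|---|---|
| 10% | 10% | 2/0.20 = 10 | 4/0.20 = 20 | 2 units more, no gain: dominated |
| 15% | 5% | 2/0.15 = 13.3 | 4/0.25 = 16.0 | 2/0.10 = 20 |
| 10% | 0% | 2/0.20 = 10 | 4/0.30 = 13.3 | 2/0.10 = 20 |
| 20% | 0% | 2/0.10 = 20 | 4/0.30 = 13.3 | 2/0.20 = 10 |

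Only the first row uses the planning rates as they stand. The others are illustrations.

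In the second row, the average ratios place four applications behind two. They leave out the 20 units per extra complication prevented, which a funder would have to weigh. In the first row, the extra visits prevent nothing, and the ratio of 20 does not reveal this.

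**How far the tilt goes**

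Four applications show the better average ratio when (p0 − p4)/(p0 − p2) exceeds C4/C2. The left side is largest at p4 = 0, where it equals p0/(p0 − p2):

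- p2 = 5%: 0.30/0.25 = 1.2
- p2 = 10%: 0.30/0.20 = 1.5
- p2 = 15%: 0.30/0.15 = 2

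So with two applications at 10%, four can look better only if the cost ratio is below 1.5. At a cost ratio of 2, four can look better once p2 exceeds 15%.

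Costs per child that do not depend on the number of applications lower the cost ratio. With fixed cost F in the same units, it is (F + 4)/(F + 2), which is below 1.5 when F exceeds 2. At F = 4 the ratio is 8/6 = 1.33, and four applications look better if p4 is below 0.30 − 1.333 × 0.20 = 3.3%. At F = 6 it is 10/8 = 1.25, and the limit is 0.30 − 1.25 × 0.20 = 5%.

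**Sampling variation**

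A simulation of 400,000 trials used 49 children per group, true rates of 30%, 10% and 10%, and a cost ratio of 2. Four applications showed the better average ratio in about 12% of trials when each schedule was set against its own placebo group, and in about 3% when the placebo groups were pooled. The choice of reference therefore matters in itself.

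The tooth-level ratio has no planning rate, so none of these limits can be calculated for it.

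**The case against.** The strongest reply is that II.F does not say that each protocol gets its own ratio, that placebo is the comparator, or that protocols will be ranked by it. An incremental ratio is also expressed in euros per complication prevented. The Sample size calculation section counts nine comparisons, more than the four pairings of an active group with the placebo group on its own schedule. Contrasts between active groups may therefore be intended. Comparator and intervals are details that an SAP or economic plan, not shown here, commonly supplies. The incremental figure could also be rebuilt from reported results: at 15% and 5%, 2/(4/16.0 − 2/13.3) = 2/(0.25 − 0.15) = 20. The anonymised data and analysis script are to be published.

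Much of this stands. The average ratio is the natural reading, not an express statement, and nothing says that the policy report must rest on it. At the planning rates as written, 10% under both schedules, average and incremental analysis agree in favouring two applications. The assumed cost ratio of 2 is not in the documents. The baseline examination, advice to parents and control examination do not scale with applications, and the protocol does not say whether they count.

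It does not remove the point. II.F states a calculation, and that calculation as worded contains no comparison between schedules, although the schedule is part of the objective. This gap does not depend on any cost assumption. That a reader could rebuild the right figure is a reason to report it.

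**Conclusion.** The point holds as a choice of method that should be improved for one secondary outcome. Read naturally, II.F gives average ratios that tend to favour the cheaper schedule and omit the extra cost per extra complication prevented. With one unit per application and 30% on placebo, the size is 13.3 against 16.0 on the average ratio, with an unreported incremental figure of 20, at rates of 15% and 5%. At 10% in both, a dominated schedule shows a ratio of 20.

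A reader might go further and infer that the ratio can never favour four applications, so that the schedule verdict is settled before any data. The documents do not support this. It would need the two-application rate to stay below 15% at a cost ratio of 2, or the cost ratio to exceed 1.5 at a rate of 10%. The first is a planning expectation that the data may overturn, and the protocol gives no costs to establish the second. At 20% and 0%, four applications show the better ratio even at double the cost. For the tooth-level ratio nothing of the kind can be shown.

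The primary outcomes and their analysis are not affected.

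**What to change.** In II.F, keep the cost per protocol and, if wanted, the ratio against placebo as description. Base the cost-effectiveness conclusion on an incremental analysis, in one paragraph of the protocol or SAP:

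- State which costs count, including those that do not depend on the number of applications.
- Measure all effects from one common reference, for example the pooled placebo groups. The difference between two active protocols then reduces to the difference in their own complication rates.
- Order the protocols by mean cost per child and remove those that cost more and prevent no more.
- Between successive remaining protocols, report the incremental cost per additional child free of major complications, with bootstrap intervals. Do the same per lesion progression avoided.

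No new data are needed. The cost is slightly more analysis. Where two protocols have nearly equal effects, the incremental interval may be wide or the ratio undefined, so the cost and effect differences should be shown beside it.

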1. arresting of the lesions – restorative treatment may no longer be necessary, but, in case the child are waiting for treatment under GA, they will not lose their place, and restorative treatment will be offered if parents will still want it because of esthetic reasons;
2. staining of the teeth – when lesion is arrested, damaged dental enamel and dentine often change colour, become darker, and the treatment methods can facilitate that (especially SDF), and therefore the teeth can become unattractive;
3. unpleasant taste during the procedure.

[figure not shown]

Fig 2. Flow chart of the clinical trial.

If the parents agree to the study, they will be assigned an appointment with one of two calibrated examiners, who will again explain the study and in whose presence, they will sign the informed consent form. If the parents for some reason decide not to participate, they can withdraw without any negative consequences. The calibrated specialist will perform a damage progression and activity register (ICDAS, Nyvad criteria) and draw lots with a closed envelope, of which group the patient will be included in (with a color code).

The patient, with information about their group's color goes to another office, where one of four trained dentists and assistants will be working (Intervention staff - IS). They will be informed about the medication to be used in each of the groups. The corresponding treatment method will be applied, and the child will be asked to describe their feelings during the procedure by using visual

analogue scale (VAS), the next visit will be set according to the group's corresponding protocol. On all future treatment appointments, the patient will only see the dentists and assistants of IS.

After the last application foreseen in the protocol, the patient will be assigned a control appointment, which will be 12 months after the first examination. During the control appointment one of the calibrated examiners will perform a documentation of stage and activity of carious lesions, not knowing which treatment had been applied. The questionnaires for the parents and children about their satisfaction with the appearance of their teeth will be applied.

Interventions

Patients who agree to participate in the study, will be randomly placed into one of six groups:

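### Side effects are asked about once, at 12 months, so transient effects other than hurt rest on long parental recall, and the recall gap differs by application schedule

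*Protocol*

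**What the plan says.** Under Outcome measures, secondary outcome II.G is "undesirable side effects, assessed by parents’ questionnaire at the 12 months follow-up visit". The section on randomization, allocation and blinding places the control appointment by reference to entry, "which will be 12 months after the first examination", not by reference to the last application.

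The Interventions section has two schedules. One is illustrated by "placebo varnish application twice with a six-month interval", the other by "Riva Star SDF application four times with a week's interval". Each of placebo, SDF and Tiefenfluorid is given on both.

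Outcome II.E, the child's three-option hurt rating, is taken at every appointment, and its timing confirms the visit dates: it "can be assessed at baseline, 1, 2, 3 weeks and 12 months; or at baseline, 6 and 12 months".

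Two other records bear on harms. WP2 (D2.3) and WP4 (task 5, D4.5) provide a form for emergency treatment. WP4 (D4.4) lists "Intervention registration forms (including Visual Analogue Scale [VAS] of patient satisfaction" and names no side-effect item. The Safety section lists the two active products and their registered use, and sets no collection of adverse effects.

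The information given to parents lists two unwanted effects: darkening of the teeth, and a bad taste while the product is applied.

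**The concern.** The timing and instrument of an outcome are fixed in the protocol, and an analysis plan cannot repair them afterwards. A parent asked at 12 months about a short-lived effect has to think back many months, and how far back depends on the child's schedule. Parents of children who do not attend are not asked at all, although those children were treated and seen at application visits.

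The introduction gives potential side-effects as one reason for the trial, and says that Tiefenfluorid has not been studied in primary teeth and that application intervals other than yearly or twice-yearly are unexplored. Counts of transient effects that are too low, or not comparable between schedules, would weaken that part of the trial's information.

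**Working it through.** **Inputs**
- Weekly groups (2, 4, 6): four applications one week apart (Interventions).
- Six-monthly groups (1, 3, 5): two applications six months apart (Interventions).
- II.G asked once, 12 months after the first examination (Outcome measures; Randomization, allocation and blinding).
- 70 children per group, 420 in all, 30% loss allowed for (Sample size calculation; Risks 1b).
- Assumption: the first application takes place at about the first examination, as the baseline time in II.E implies.

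**Reproducing the plan's figures**
Four applications a week apart fall at weeks 0, 1, 2 and 3. Two applications six months apart fall at months 0 and 6. Both match the visit times in II.E. For attendance, 70 × (1 − 0.30) = 49 children per group, the number in Risks 1b.

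**Gap from last application to the question**
12 months = 365.25 / 7 = 52.2 weeks.
- Weekly: 52.2 − 3 = 49.2 weeks.
- Six-monthly: 52.2 / 2 = 26.1 weeks.
- Difference 49.2 − 26.1 = 23.1 weeks; ratio 49.2 / 26.1 = 1.9.

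**Gap averaged over all applications**
- Weekly: (52.2 + 51.2 + 50.2 + 49.2) / 4 = 50.7 weeks.
- Six-monthly: (52.2 + 26.1) / 2 = 39.1 weeks.
- Difference 11.6 weeks, about half the difference at the last application. The first application is about a year back in every group.

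**Children without II.G**
0.30 × 420 = 126, or 21 per group.

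**What unequal recall could do (illustration only)**
The document gives neither a side-effect rate nor a recall rate. Assume that 30% of children in both schedules truly have a transient effect, and that observed rate = true rate × proportion recalled.

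| Recall, weekly | Recall, six-monthly | Observed, weekly | Observed, six-monthly |
|---|---|---|---|
| 90% | 95% | 27.0% | 28.5% |
| 70% | 85% | 21.0% | 25.5% |
| 50% | 75% | 15.0% | 22.5% |

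The false difference runs from 1.5 to 7.5 percentage points. These rows assume that a longer gap means poorer recall. If four applications in close succession were better remembered than two, the recall figures in a row would swap, and so would the sign of the difference.

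**Which comparisons are affected**
SDF, Tiefenfluorid and placebo on the same schedule share the same gap, so poor recall there mainly lowers all the counts. Only weekly against six-monthly comparisons have unequal gaps.

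**The case against.** A reader might infer that no harms are recorded before month 12, or that 126 children would yield no safety data. The documents do not support either reading. Hurt is rated at each appointment under II.E, and emergency treatment goes on its own form as it happens. Children who miss the last visit would lack II.G, but not the hurt ratings from visits they attended. The 30% is also a planning allowance, not a forecast for this outcome.

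A reader might also infer that the weekly schedule will look safer simply because more time has passed. That does not follow. Weekly children have four exposures against two, which gives parents more to report, and the averaged gaps differ much less than the gaps from the last application. The net direction is undetermined.

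Further points on the other side have weight. WP4's objective on side-effects mentions staining and names the products, not the schedules, and staining is properly assessed at 12 months. Each schedule has its own placebo group. Of the transient effects one might list, only taste is named in the protocol. The list of contents for D4.4 is not exhaustive, and the questionnaires are not available, so their wording and recall window cannot be checked.

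What stands is that II.G as defined is not limited to staining, and that its one stated time of collection is month 12. No visible text sets a side-effect question at the application visits. A hurt rating does not measure taste, and an emergency form does not register effects that needed no emergency care.

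**Conclusion.** The point holds in a limited form. Transient effects other than hurt are collected only by parental recall at 12 months, about 49 weeks after the last weekly application and about 26 weeks after the last six-monthly one (50.7 against 39.1 weeks over all applications). II.G would be missing for 126 of 420 children if the planned loss occurs. Within-schedule comparisons suffer mainly from under-reporting; between-schedule comparisons of transient effects may also be biased, in an unknown direction.

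The gaps follow from the protocol's own dates, given a first application at about the first examination. That recall over such periods is incomplete is an inference, and its extent cannot be computed from the document. The primary outcomes are not touched and nothing in the text is contradictory. This is a design weakness in a secondary outcome, cheap to correct while children are being treated and not recoverable afterwards.

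**What to change.** Amend II.G and the intervention registration form (D4.4):

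- Add one short side-effect question in fixed wording, answered by the parent or child and recorded on the day of each application.
- Compare agents and schedules on this same-day record, in all treated children.
- Report it per application and per child, because the number of applications differs (four against two), and use the first application as the like-for-like comparison.
- If an item on effects since the previous application is wanted, keep it descriptive or give it the same fixed recall window in all groups. Asked simply at the next visit, it would cover one week in the weekly groups and six months in the others, which would bring back unequal recall.
- Keep the 12-month questionnaire for lasting effects such as staining.

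No application schedule or clinical procedure changes. The cost is about a minute at visits that already take place. The main drawback is that the intervention staff, who know the product, would do the recording. Fixed wording and the parent's or child's own answer limit this but do not remove it.
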